14.2.7 Imputation for Dates

More generally, in the case of partial adverse event onset date or date of death, the unknown portion of the date of the event will be imputed. If the month and year are known, the 15th of the month will be used for analysis. If only the year is known, the event will be analyzed as if it occurred on June 30th of the known year. In the rare case that the date is fully unknown, the date will be imputed as the index procedure date. Imputation of partial dates is subject to the condition that it must occur on or after the index procedure date. In the case where the imputed date is before the index procedure date, the date of the index procedure will be used. As death cannot occur before any documented subject contact, for date of death, the imputed date of death must occur on

or after the last known contact in the study.

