3.3.1 Primary Endpoints

Primary Safety Endpoint:

- Freedom from major complications of the target limb access site within 30 days post-procedure which includes the following:

Major Complications:

- Vascular injury attributable to the investigational device that requires surgical repair, stent-graft, or balloon angioplasty
- Access site-related bleeding attributable to the investigational device that requires transfusion
- Any new access site-related ipsilateral lower extremity ischemia attributable to the investigational device and documented by patient symptoms, physical exam, and/or decreased or absent blood flow on lower extremity angiogram
- Surgery for access site-related nerve injury attributable to the investigational device
- Permanent (lasting > 30 days) access site-related nerve injury attributable to the investigational device
- Access site infection requiring intravenous antibiotics and/or extended hospitalization

Primary Efficacy Endpoint:

- The mean TTH in the Common Femoral Artery (CFA) of the target limb access site with use of the investigational device.

TTH will be evaluated from time of procedural sheath removal to first observed cessation of CFA bleeding (excluding cutaneous or subcutaneous oozing at access site) in the target limb for subjects not requiring adjunctive intervention.

If a sheathless system is used during the procedure, TTH will be calculated from final introducer sheath removal to first observed cessation of CFA bleeding (excluding cutaneous or subcutaneous oozing at access site) in the target limb for subjects not requiring adjunctive intervention.

Adjunctive Intervention is defined as any use of surgical or endovascular intervention OR firm/occlusive manual pressure needed to achieve access site hemostasis (light/non-occlusive pressure to control cutaneous or subcutaneous oozing at the access site is excluded).

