7.5.4 Unscheduled Visit

The unscheduled visit is designed to evaluate the ongoing safety of enrolled patients outside the protocol defined 30-day and/or 60-day visits.

Patients with missed or incomplete in-person protocol defined visits due to the COVID-19 pandemic will not be considered lost-to-follow-up/withdrawn by the Sponsor. Rather, the unscheduled visit can be used to reconsent the patient for this extended follow up to

evaluate their safety. The Interim follow up visit will be available for up to 12 months from the primary study index procedure and subjects should return as soon as reasonably possible unless the patient wishes to be withdrawn from the study.

The following data will be collected during the unscheduled visit:

- DUS for assessment of groin/access site related complications in target limb only (if not completed already or if repeat is needed (e.g., missed 30-day and/or 60-day visit))
- Targeted physical exam, including groin exam (if not completed already or if repeat is needed (e.g., missed 30-day and/or 60-day visit))
- Concomitant Medications (Anticoagulation / Antiplatelets Only)
- Adverse Events

If the patient will not or cannot return for an unscheduled visit, the study site should contact the patient via telephone to determine AEs and patient condition.

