14.2.1.2 Study Visit

Study visit Day 0 is the date of the index procedure. Day in the study will be calculated relative to the index procedure as follows:

Study Day = Assessment Date – Index Procedure Date

Each subject duration in the study will be based on the last study contact date, which is the latest date of all follow-up visits, assessments, adverse event onset or resolution, and study exit, including date of death.

Duration will be calculated as follows: Duration Days = Start Date – End Date

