#### 7.4.3 Imputation for Dates

More generally, in the case of partial adverse event onset date or date of death, the unknown portion of the date of the event will be imputed. If the month and year are known, the 15th of the month will be used for analysis. If only the year is known, the event will be analyzed as if it occurred on June 30th of the known year. In the rare case that the date is fully unknown, the date will be imputed as the index procedure date. Imputation of partial dates is subject to the condition that it must occur on or after the index procedure date. In the case where the imputed date is before the index procedure date, the date of the index procedure will be used. As death cannot occur before any documented subject contact, for date of death, the imputed date of death must occur on or after the last known contact in the study.

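### The partial-date rule can place a true 30-day major complication after day 30 and score it event-free, while a wholly unknown date counts as a failure

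*Protocol*

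**What the plan says.** The primary safety endpoint (Protocol 3.3.1, SAP 5.1.1) is "Freedom from major complications of the target limb access site within 30 days post-procedure". Days are counted as "Study Day = Assessment Date – Index Procedure Date" (Protocol 14.2.1.2), with the index procedure on day 0.

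Protocol 14.2.7, repeated in SAP 7.4.3, fills in incomplete adverse event onset dates by how much is known:

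- Month and year: "If the month and year are known, the 15th of the month will be used for analysis".
- Year only: "If only the year is known, the event will be analyzed as if it occurred on June 30th of the known year".
- Nothing: "In the rare case that the date is fully unknown, the date will be imputed as the index procedure date".

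For adverse events the only constraint is a floor: "In the case where the imputed date is before the index procedure date, the date of the index procedure will be used". Neither document caps the imputed date, even at the visit where the event was reported, and neither exempts primary endpoint events.

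The follow-up matters too. Under the pandemic provisions in Protocol 7.5.4, "The Interim follow up visit will be available for up to 12 months from the primary study index procedure", with a telephone call for patients who cannot return.

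**The concern.** The endpoint is a yes/no count with a cut at day 30, so for any event with a partial date the imputation rule decides whether it counts. A mid-month or mid-year date can fall beyond the cut when the event did not.

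The rule is also out of order. It is strict when nothing is known (day 0, a failure) but can be lenient when the year or month is known. More information can thus turn a failure into an event-free subject.

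Recall many months after the procedure makes partial dates more plausible. At the decision boundary, one reclassified subject reverses the safety conclusion.

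**Working it through.** **Inputs.** The window is days 0 to 30, with the date rules and index-date floor above. The safety goal is 85.2%, the assumed event-free rate 94% and one-sided alpha 0.05 (Protocol 14.1.2). Success requires a one-sided 95% Clopper-Pearson lower limit above 85.2% (Protocol 14.2.10.2, SAP 7.7.2).

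**1. The plan's safety figures reproduce.** For X ~ Binomial(N, p), alpha = P(X ≥ r | p = 0.852) and power = P(X ≥ r | p = 0.94).

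| N | r | alpha | power | stated power |
|---|---|---|---|---|
| 78 | 72 | 0.0458 | 0.8130 | 81.3% |
| 86 | 79 | 0.0486 | 0.8558 | 85.6% |
| 95 | 87 | 0.0469 | 0.8833 | 88.3% |

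**2. Worked dates.** Imputed day = max(imputed date, index date) − index date.

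| Index | True onset | Known part | Imputed date | Imputed day |
|---|---|---|---|---|
| 10 Jan 2019 | 5 Feb 2019 (day 26) | month and year | 15 Feb 2019 | 36, outside |
| 10 Jan 2019 | 12 Jan 2019 (day 2) | year | 30 Jun 2019 | 171, outside |
| 10 Dec 2019 | 5 Jan 2020 (day 26) | month and year | 15 Jan 2020 | 36, outside |
| 10 Jan 2019 | any | nothing | 10 Jan 2019 | 0, counted |

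If the first event were reported at a visit on 9 February (day 30), its imputed onset of 15 February would fall after the report.

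**3. How often, given a partial date.** Every index date in 2019 was crossed with every true event day. Weighting these equally is an assumption (uniform timing).

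| True day | Error | Month known | Year only |
|---|---|---|---|
| 0–30 | moved out | 1,260/11,315 = 11.1% | 5,115/11,315 = 45.2% |
| 0–7 | moved out | 0/2,920 = 0% | 1,228/2,920 = 42.1% |
| 8–30 | moved out | 1,260/8,395 = 15.0% | 3,887/8,395 = 46.3% |
| 31–60 | pulled in | 1,523/10,950 = 13.9% | 5,085/10,950 = 46.4% |

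With 2020 index dates the results are almost the same. Simulating early onset instead (exponential, mean 5 days) moves out 0.6% of month-known and 42.5% of year-only events.

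**4. What one event does at the boundary.** The Clopper-Pearson lower limit is the 5% quantile of Beta(x, N − x + 1), with x subjects event-free.

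| N | One short | Lower limit | At threshold | Lower limit |
|---|---|---|---|---|
| 78 | 71 | 83.8%, fail | 72 | 85.4%, pass |
| 86 | 78 | 83.8%, fail | 79 | 85.3%, pass |
| 95 | 86 | 84.1%, fail | 87 | 85.3%, pass |

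**5. How likely that is.** At a true 94% rate, the chance of being exactly one short is 9.1% (N = 78), 7.1% (86) and 5.8% (95). The documents give no frequency of partial dates, so assume 1% to 5% of major events are month-only. At N = 78, one short means 7 events, and the chance that this happens and at least one moves out is 0.0914 × [1 − (1 − q × 0.111)^7]. That gives 0.07% for q = 0.01 and 0.35% for q = 0.05.

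**The case against.** The best defence is that this will seldom arise. Most major complications (surgical repair, stent-graft, transfusion, intravenous antibiotics, extended hospitalization) leave dated records. The protocol provides source verification (section 11) and CEC classification (8.7). Device failures, which may include use leading to a major complication (13), are reportable within 24 hours of knowledge (8.6). A year-only date for such an event is improbable, and no month-only event on days 0 to 7 is displaced. Mid-period imputation is also a common convention. All of this stands, and it limits the weight of the point.

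A second defence is that other provisions already settle 30-day status. This holds only in part. The telephone-and-record determination (Protocol 14.2.5, SAP 7.4.1) does address status at day 30 directly, but only for patients with no post-discharge visit. The CEC classifies events, but neither document says it sets onset dates or overrides the imputation. The tipping-point analysis (Protocol 14.2.6, SAP 7.4.2) covers subjects without a 30-day visit, not events with imputed dates.

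A reader might infer that the rule inflates the safety proportion. The documents do not support that. The rule also pulls later events in, and both the index-date floor and the day-0 rule are conservative. The net direction depends on how many events fall on each side of day 30, which is not given. Routine event collection ends at day 30 unless an ultrasound is repeated, which limits late events outside the extended follow-up but does not establish a direction. Nor are 11% and 45% expected error rates: they apply only once a date is partial.

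**Conclusion.** The gap is real and small. As written, the rule can place a true 30-day major complication outside the window with no stated override, and it treats a wholly unknown date more strictly than a partly known one. The result is two-way misclassification that can, but need not, favour the device.

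Given a partial date and uniform timing, about 11% of month-only and 45% of year-only in-window events move out. The overall effect is probably rare; under the assumed 1% to 5% of month-only dates, the chance of a reversed result through the one-short case at N = 78 is well below 1%. No stated alpha, power or sample size is wrong. It merits correction because a single event can decide the result at the boundary and the remedy costs little.

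**What to change.** Amend Protocol 14.2.7 and SAP 7.4.3 for major complications with a partial onset date:

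1. Determine 30-day status from source records or by the CEC.
2. If that is impossible, use the earliest date consistent with the known part, no earlier than the index date and never later than the date the event was reported.
3. Flag and list every such event.
4. Repeat the primary safety analysis under the current mid-period rule as a sensitivity analysis.

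In the same 2019 enumeration, the fallback in step 2 moves 0 of 22,630 in-window combinations (11,315 month-known and 11,315 year-only) past day 30.

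The cost is wording in two documents plus one listing and one repeat analysis. The downside is that some events truly after day 30 will count as failures. Where no other dating evidence exists, this affects 5,373/10,950 = 49% of month-only and 10,485/10,950 = 96% of year-only events on days 31 to 60. That is conservative against the performance goal, and it is why the earliest-date rule should be a fallback rather than the first step. Label: cheap improvement.

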14.2.8 Subject Disposition

Subjects who are screened and signed an informed consent form, but do not meet all protocol eligibility criteria (i.e., screening failure), will be excluded from the statistical analyses. These subjects will be summarized in a subject accountability table only.

Subject accountability will be summarized by visit for those in the FAS. The number of subjects who are enrolled, eligible for follow-up, and number completing clinical follow-up will be summarized for each protocol-required visit.

14.2.9 Demographics and Baseline Characteristics

Descriptive statistics will be presented for clinically relevant baseline demographic, medical history, and clinical characteristic variables.

14.2.10 Analysis of Study Endpoints

Study success is defined as the successful rejection of the corresponding null hypotheses for each of the primary safety and effectiveness endpoints.

14.2.10.1 Primary Efficacy Endpoint

The primary efficacy endpoint will be evaluated using the using the efficacy analysis set. The mean and standard error will be reported for the primary efficacy endpoint. A one-sample t-distribution will be used for calculating the upper 97.5% confidence limit.

14.2.10.1.1 Sensitivity Analyses

There will be three sensitivity analyses:

1. The primary efficacy endpoint analysis will be repeated with the PPS patients only if PPS_RI patients are added to the efficacy analysis set
2. Tipping analysis based on missing data in the efficacy analysis set as described in section 14.2.6
3. The primary efficacy endpoint analysis will be repeated with the PPS_RI and the efficacy analysis set combined.

14.2.10.2 Primary Safety Analysis

The primary safety endpoint will be evaluated using the FAS or the safety analysis set if roll-ins are needed. The endpoint will be presented as the proportion of subjects with

freedom from primary safety endpoint and the lower 95% confidence limit using the Clopper-Pearson exact method^{vi}. If the one-sided 95% confidence limit is greater than 85.2%, then the device will have met the performance goal for safety.

14.2.10.2.1 Sensitivity Analyses

There will be three sensitivity analyses:

1. The primary safety endpoint analysis will be repeated with the FAS patients only if FAS_RI patients are added to the safety analysis set
2. Tipping analysis based on missing data in the safety analysis set, as described in section 14.2.6.
3. The primary efficacy endpoint analysis will be repeated with the FAS_RI and the safety analysis set combined.

14.2.10.3 Secondary Endpoints

No formal hypothesis tests for the secondary and exploratory endpoints will be performed; endpoints will be summarized using the FAS with descriptive statistics.

14.2.11 Subgroup Analyses

Subgroup analysis of the primary safety (major and minor complications analyzed separately) and efficacy endpoints will be performed for the following subgroups: gender, age (Age<65, Age≥65), and race (white vs. non-white). These analyses are intended to assess the consistency of results across subgroups.

Subgroup analyses will be performed using the efficacy analysis set for the primary efficacy endpoint and the safety analysis set for the primary safety endpoint. For each subgroup, a regression model will be fit that includes fixed effects for subgroup membership.

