1.5.2 CE Study

The CE study was a prospective, multi-center, and single arm study conducted in OUS countries. The primary endpoint of effectiveness was technical success defined as closure of the arteriotomy without the need for any access-site-related adjunctive surgical or endovascular procedures. The primary endpoint of safety was freedom from major VARC-2 events within 30 days of the procedure. Results are demonstrated as shown in **Table 2**.

A total of twenty-six (26) subjects were enrolled across 5 sites in Australia (1), New Zealand (3), and Taiwan (1), between May 30, 2017 and January 12, 2018. Study results from the total of 26 patients' data were monitored and shown in **Table 2**.

The patient population consisted of 20 (77%) men and 6 (23%) women with a mean age of 76.5 years (range 33 – 91 years) and mean BMI is 25.7 (range 20.7-36.7). The mean estimated diameter of femoral artery lumen at the closure site was 8.3 mm and ranged from 6 mm to 11 mm as measure by ultrasound or CT scan. The introducer sheath utilized in study subjects ranged from 8Fr to 18Fr. An 8Fr introducer sheath was utilized in 1 (3.85%) subject, 9Fr introducer sheath was utilized in 1 (3.85%) subject, 10Fr introducer sheaths were utilized in 3 (11.54%) subjects, 12Fr introducer sheaths were utilized in 5 (19.23%) subjects, 14Fr introducer sheaths were utilized in 7 (26.92%) subjects, 16Fr introducer sheaths were utilized in 3 (11.54%) subjects and 18Fr introducer sheaths were utilized in 6 (23.08%) subjects. The mean TTH was 1 minute and 11 seconds (range 00:01 – 11:54). The mean estimated total blood loss including the interventional procedure was 158 ml (range 5 – 600 ml).

A successful ipsilateral “pre-close” percutaneous technique, defined as closure with the Cross-Seal™ System, was achieved in 100% of the subjects with no major ipsilateral access site vascular complication at 30 days follow-up.

Table 2. Summary of CE Clinical Study of the Cross-Seal™ System (GEN 2.0)

Patient Population	
Gender	20 (77%) men and 6 (23%) women
Age	Mean age = 76.5 years (range 33 - 91 years)
BMI	Mean BMI = 25.7 (range 20.7 - 36.7)

Diameter of femoral artery lumen	Mean = 8.3 mm (range 6.0 - 11.0 mm)	
Procedure		
Introducer size	8 Fr, n = 1 9 Fr, n = 1 10 Fr, n = 3 12 Fr, n = 5	14 Fr, n = 7 16 Fr, n = 3 18 Fr, n = 6
TTH	Mean = 1:11 minutes (range 00:01 - 11:54)	
Total estimated blood loss	Mean = 158 mL (range 5 -600 mL)	
Technical Success*	100%	
Post-procedure		

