9.2 Potential Benefits

Subjects enrolled in this clinical study will be monitored closely throughout the study and have regular assessments according to the investigator's standards of care. The data collected during the clinical study will provide further understanding how the Cross-Seal™ System is clinically beneficial. Potential benefits may include:

- Reduced Time-to-Ambulation (TTA)
- Reduced Time-to-Hemostasis (TTH)
- Improved quality of life

10 Centers for Medicare and Medicaid Services (CMS) Reimbursement

The Sponsor will seek applicable Medicare coverage in compliance with CMS requirements for this study. Based on the target study population including mean age, approximately 70% of subjects enrolled in this study will utilize CMS/Medicare reimbursement during their participation.

The study will be conducted in compliance with all applicable Federal regulations concerning the protection of human subjects found at 21 CFR parts 50, 56, and 812, and 45 CFR part 46. In addition, the study will be registered with the National Institutes of Health National Library of Medicine's ClinicalTrials.gov.

The Sponsor has a legal responsibility to the regulatory authorities to fully report all results of sponsored clinical studies. No investigational procedures other than those in this protocol shall be undertaken. The sponsor intends to submit a formal report to FDA following completion of the last subject visit required for primary endpoint analysis. Should the study be terminated early, the Sponsor will make every effort to expedite reporting of study

results to the FDA database for public review. Any use of the investigational device by an investigator that is contradictory to the application described in the IFU will be categorized as device misuse.

11 Monitoring

The Sponsor will perform monitoring functions within this clinical study and may be delegated to a CRO designate as needed. Study monitors will work in accordance with standard operating procedures (SOPs) and the approved Monitoring Plan. Any CRO monitors have the same rights and responsibilities as monitors from the Sponsor organization.

At the site, monitors will perform and verify the following:

- The adequacy and experience of the study center including Sponsor notification of any problems relating to facilities, technical equipment or medical staff

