14.1.1 Primary Efficacy Endpoint

The primary effectiveness hypothesis will be tested by comparing the primary effectiveness endpoint, mean time-to-hemostasis (TTH), against a performance goal (PG) of 15 minutes.

The comparison to the performance goal will be based on the following statistical hypothesis test:

$$H_0: \mu_{TTH} \geq 15$$

$$H_A: \mu_{TTH} < 15$$

where μ_{TTH} is the mean time-to-hemostasis in minutes.

The test will be based on whether the upper one-sided 97.5% confidence limit (based on a t-distribution)^{iv} is less than 15. Assuming similar performance to Perclose ProGlide®, with a mean time-to-hemostasis of 9.8 minutes and a standard deviation of 17 minutes the sample sizes for power levels from 80 to 90%

a Table 3: Primary Efficacy Endpoint Sample Sizes for Various levels of Power

Power	Sample Size	Maximum Observed Time (minutes) and still reject H_0
80.0%	86	10.8
81.4%	89	10.9
82.3%	91	10.9
83.1%	93	10.9
84.3%	96	11.0
85.0%	98	11.1

Successful rejection of the null hypothesis will mean that the PG has been met.

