14.2.1.4 Statistical Significance

Unless otherwise specified, hypothesis testing will be performed at the two-sided 0.05 significance level. P-values will be rounded to three decimal places. If a p-value is less

than 0.001 will be reported as "<0.001". If a p-value is greater than 0.999, it will be reported as ">0.999".

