##### Summary Statements

Statistical Analysis Plan		Page 26 of 31
Sponsor Terumo Medical Corporation	Study Cross-Seal IDE Trial: Prospective, Multi-Center, Single Arm Study of the Cross-Seal Suture-Mediated Vascular Closure Device System	Version 1.4

A sample size of 86 achieves 80% power to detect non-inferiority using a one-sided one-sample t-test when the non-inferiority mean is 15.0 and the actual mean is 9.8. The data are drawn from a single population with an estimated standard deviation of 17.0. The significance level (alpha) of the test is 0.025.

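### Time-to-hemostasis is checked against age only through a split at 65; against a linear trend that age in years would detect with 80% power, the split gives up about 19 to 29 points

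*Protocol*

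**What the plan says.** Protocol 14.2.11 and SAP 7.8 carry the same text. The factors are "gender, age (Age<65, Age≥65), and race (white vs. non-white", and for each of them "a regression model will be fit that includes fixed effects for subgroup membership". The aim is given as follows: "These analyses are intended to assess the consistency of results across subgroups". No power, threshold or follow-up action is attached. If a p-value is read, the default in Protocol 14.2.1.4 applies: "hypothesis testing will be performed at the two-sided 0.05 significance level".

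Neither document fits age in years, gives a reason for using 65 in the model, or states an age SD or an expected mean age for this trial. Demographics are collected at baseline (Protocol 7.1 and 7.6), so age in years should already be on file.

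The clues to the age mix are indirect. The CE study of 26 subjects had a "mean age of 76.5 years", range 33 to 91 (Protocol 1.5.2). The first-in-human study of 10 subjects had a mean of 66.0, range 56.3 to 80.2 (Protocol 1.5.1). Protocol Section 10 expects that "approximately 70% of subjects enrolled in this study will utilize CMS/Medicare reimbursement during their participation".

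**The concern.** A two-level factor treats a subject of 66 and one of 91 as the same. If TTH lengthens with age, much of that change could fall among the older subjects, where the factor cannot see it. A cut away from the middle of the age distribution also leaves a small younger group and a noisy contrast. The analysis could then show no clear difference by age even if a sizeable trend were present, and a reader could take that as evidence of consistency. What is at stake is how informative a supportive analysis is, not the trial's conclusion.

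**Working it through.** **The plan's own figure first.** Protocol 14.1.1 plans "with a mean time-to-hemostasis of 9.8 minutes and a standard deviation of 17 minutes" against a goal of 15, one-sided 0.025. At N = 86 the noncentrality is (15 − 9.8)/17 × √86 = 2.84 on 85 df, which gives power 0.8008. This matches the SAP appendix: "A sample size of 86 achieves 80% power to detect non-inferiority using a one-sided one-sample t-test". The plan states no power for the age analysis, so the rest is new calculation.

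**Inputs.** TTH SD 17 minutes; two-sided 0.05; N = 86 and 96, both from the SAP sample-size table. Assumed: a linear age trend and normally distributed age.

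**Reference trend.** For age in years to have 80% power, the noncentrality λ must be 2.834 (N = 86) or 2.831 (N = 96). The slope per SD of age is λ × 17/√N:
- N = 86: 2.834 × 17/9.27 = 5.2 minutes
- N = 96: 2.831 × 17/9.80 = 4.9 minutes

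**Loss from the split.** If the cut lies c SD below the mean age and p is the share below it, λ shrinks by r = φ(c)/√(p(1 − p)). Three readings of the documents place the cut:
- First-in-human: the expected range of 10 normal values is 3.08 SD, so SD ≈ 23.9/3.08 = 7.8 and c = (66.0 − 65)/7.8 = 0.13.
- Medicare: reading 70% Medicare use as 70% aged 65 or over gives p = 0.30 and c = 0.52.
- CE: the expected range of 26 normal values is 3.96 SD, so SD ≈ 58/3.96 = 14.6 and c = (76.5 − 65)/14.6 = 0.79.

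| Age mix | c | Share under 65 | r | Power of split | Loss (points) |
|---|---|---|---|---|---|
| First-in-human | 0.13 | 45% | 0.796 | 60.6% | 19.4 |
| Medicare | 0.52 | 30% | 0.759 | 56.6% | 23.4 |
| CE | 0.79 | 21.5% | 0.711 | 51.3% | 28.7 |

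These results are the same at N = 86 and N = 96 to within a tenth of a point.

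**Sensitivity.**
- *Fewer under 65* (no figure in the documents supports these shares): 15.9% loses 34.2 points, 12.5% loses 38.5 and 8% loses 46.4.
- *Half the trend*: age in years has 28.8% power. The split has 20.0%, 18.6% and 16.9% under the three mixes, so the loss is about 9 to 12 points. It reaches 17 only at 8% under 65.
- *Skewness* (simulation, N = 86, 20,000 trials each): with normal age and TTH, the three mixes lose 19.6, 24.7 and 29.9 points. With skewed TTH they lose 16.6, 19.5 and 24.2. With left-skewed age around 76.5 (SD 11.5 to 14.7) and skewed TTH, the loss is 18 to 20.

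**Detectable group difference at 80% power**, λ × 17 × √(1/n₁ + 1/n₂):
- N = 96: 29 v 67 gives 10.7 minutes; 19 v 77 gives 12.3.
- N = 86: 26 v 60 gives 11.3 minutes; 17 v 69 gives 13.0.

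These should not be set beside a slope per decade. The groups' mean ages differ by φ(c)/(p(1 − p)) SD, which is 1.66 SD at 30% under 65 and 1.75 SD at 20%. The reference slope of 4.9 to 5.2 minutes per SD therefore implies a group difference of 8.1 to 9.1 minutes. The like-for-like comparison is about 8 to 9 minutes against 11 to 13.

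**The case against.** The best case for leaving the plan alone has four parts.

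- **Nothing depends on the analysis.** It has no threshold or action, unlike the site-poolability model in Protocol 14.2.3, which has a 0.15 trigger. Study success rests on the two primary tests alone (Protocol 14.2.10). This stands and limits the point to an inexpensive improvement.
- **The reference trend is large.** About 5 minutes per SD of age is close to the whole 5.2-minute gap between the assumed mean and the performance goal. For half that trend both models are weak, and a non-significant slope could be misread just as easily. This also stands, and it is why the fix turns on the interval rather than on a p-value.
- **The assumptions are rough.** CE ages run 43.5 years below the mean and only 14.5 above it, so they are not symmetric. A non-negative TTH with mean 9.8 and SD 17 must be right-skewed. Allowing for both reduces the loss but does not remove it.
- **A slope has its own weakness.** It assumes rough linearity, and a few very young subjects could drive it (the CE minimum was 33). This stands as a cost.

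A reader might go further and infer that 65 lies about one SD below the expected mean age, that nearly everyone falls in one group, and that the loss could reach 46 points. The documents do not support this. They give neither an expected mean nor an SD. The Medicare figure, read as age, leaves 30% under 65. The 46-point end needs about 8% under 65, and no figure in the documents points there.

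**Conclusion.** The point holds as a modest, optional improvement. The only age model for TTH is a split at 65. Against a linear trend that age in years would detect with 80% power, the split has about 51% to 61% power, a loss of about 19 to 29 points. This rests on a linear trend, roughly normal age, and age mixes inferred from two small earlier studies and a reimbursement estimate. Skewness brings the loss to about 17 to 24 points, depending on the mix, and a trend half as large to about 9 to 12. A share under 65 below about 20% would push it above 30.

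It would be too strong to say that the split can find nothing, since 11 to 13 minutes is an 80%-power mark and not a limit. It would also be too strong to say that the plan will declare consistency from a non-significant result, because it contains no such rule.

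**What to change.** In Protocol 14.2.11 and SAP 7.8, keep the descriptive display for the two age groups. Add one sentence: TTH will also be regressed on age in years in the efficacy analysis set, the slope per decade will be reported with its 95% confidence interval, and consistency by age will be judged from that interval rather than from the absence of significance.

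Check linearity with a plot of TTH against age or a quadratic term; two group means always fit a line and cannot check it. State whether the slope depends on a few very young subjects.

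The cost is a sentence and one model on data already collected. The interval will still be wide: its half-width is about 1.99 × 17/√86 = 3.6 minutes per SD of age (3.4 at N = 96). A moderate trend may therefore remain unresolved, but the report would show that openly. The primary tests, the sample size and the definition of study success do not change.
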